Insufficient sleep and sleep irregularity (variability in sleep duration) are increasingly recognized as important contributors to glycemic control and diabetes distress in type 1 diabetes (T1D). Up to 40% of adults with T1D had a sleep duration < 6-6.5 hours per night, either by self-report or objectively assessed actigraphy. Diabetes distress is reported (40% prevalence) in individuals with T1D and is associated with poor glycemic control. Despite findings that sleep disturbances are common in T1D, our present understanding of the effects of sleep optimization on sleep, diabetes distress, and glycemic control is limited. The purpose of this pilot and feasibility trial is to evaluate the effects of a T1D-specific sleep optimization intervention (Sleep-Opt-In) on the outcomes of sleep, diabetes distress and glycemic control in individuals with T1D and habitual short sleep. We specifically aim to determine if Sleep-Opt-In will: 1) be feasible and acceptable to the target population; 2) result in improved sleep duration and regularity; 3) result in improved glycemic control; and 4) lower diabetes distress. To achieve these aims, we propose a randomized controlled trial in 20 adults aged 18 to 65 years with T1D. Participants will be screened for habitual sleep duration < 6.5 hours per night. Eligible subjects will be randomized to the T1D-Sleep-Opt-In group or attention control group. A one-week run-in period is planned, with baseline measures of sleep (duration and regularity), glycemia (A1C, fructosamine, glycemic variability), and diabetes distress (Diabetes Distress Scale). The T1D-Sleep-Opt-In will entail a novel technology-assisted behavioral sleep extension intervention that we recently developed to leverage rapidly increasing public interest in sleep tracking by consumers (+500% in 3 years). Our technology employs four elements: a wearable sleep tracker, didactic content, an interactive smartphone application, and brief telephone counseling. For this proposal, we will further optimize our intervention to be T1D-specific by addressing T1D-related sleep issues such as nocturnal hypoglycemia. The attention control group will participate in a healthy living information program. At completion (Week 8) and post-program, baseline measures will be repeated to determine differences between the two groups (Week 12) and sustainability of the intervention (intervention group week 24). Findings from this proposed pilot study will serve as the foundation for a larger clinical trial to improve sleep, reduce diabetes distress, and improve glycemic control.

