
Specific Aims

In 2015, 1.2 million people in the U.S. had diagnosed type 1 diabetes (T1D).¹ Maintenance of glycemic control is necessary to reduce complications in T1D. Despite improvements in treatment regimens and technology, less than 31% of adults with T1D achieve glycemic targets.² Insufficient sleep and sleep irregularity are increasingly recognized as important contributors to glycemic control and diabetes distress in T1D.³⁻⁵ High levels of diabetes distress negatively impact self-management behaviors.⁶ The 2017 American Diabetes Association Standards of Medical Care in Diabetes incorporated sleep, including sleep duration and pattern, as an important component of medical evaluation in persons with diabetes.⁷ This is the first time sleep has been included in these national guidelines. Despite findings that insufficient sleep is common in T1D, our present understanding of the effects of sleep optimization on glycemic control and diabetes distress is limited.

The primary aim of this pilot trial is to evaluate the feasibility, acceptability, and preliminary efficacy of a **T1D-specific sleep optimization intervention “T1D-Sleep-Opt-In”** on the outcomes of sleep (duration and regularity), glycemic control (A1C, fructosamine, glycemic variability), and diabetes distress (Diabetes Distress Scale)⁸ in working-age adults with T1D and habitual short sleep duration. **This proposal is based on recent observations and a newly developed sleep optimization intervention from our group. (1)** Working-age adults with T1D who reported sleeping < 6h had significantly higher A1C (vs. ≥ 6h). **(2)** Sleep irregularity in T1D was associated with poor glycemic control and increased glycemic variability. **(3)** Sleep irregularity was associated with diabetes distress in T1D. **(4)** A pilot study of a 2-week behavioral sleep optimization in adults without diabetes who had habitual short sleep duration led to improved fasting insulin resistance. **(5)** A pilot trial of our newly developed technology-assisted behavioral sleep optimization intervention in adults with short sleep duration demonstrated a clinically significant increase in sleep duration (median 35 minutes). **Therefore, this proposal seeks to improve glycemic control and lower diabetes distress by improving sleep duration and regularity in T1D using T1D-Sleep-Opt-In under a randomized controlled design.**

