Our novel sleep optimization intervention employs: a wearable sleep tracker, didactic content, an interactive smartphone application, and brief telephone counseling.⁹ For this proposal, we will adapt the intervention to be T1D-specific. We will then test preliminary efficacy. We hypothesize T1D-Sleep-Opt-In will be feasible and acceptable and increase sleep duration and regularity; results will serve as pilot data for a larger trial (RFA-DK-17-028 *Treating Diabetes Distress to Improve Glycemic Outcomes in T1D*). This pilot study will randomize 20 working adults with T1D (18-65 years) who report habitual short sleep duration to eight-week T1D-Sleep-Opt-In or attention control. **Specific aims** are to determine:

Aim 1: Feasibility and acceptability of T1D-Sleep-Opt-In. **Rationale:** Analysis of recruitment, retention, and participant program evaluation will provide feasibility and acceptability data. **Hypothesis:** T1D-Sleep-Opt-In will be feasible and acceptable to the target population. **Approach:** Feasibility will be determined through analysis of recruitment and retention. Acceptability will be determined through participant evaluation.

Aim 2: Preliminary efficacy of T1D-Sleep-Opt-In on sleep duration and regularity. **Rationale:** Our sleep optimization intervention resulted in increased sleep duration in non-T1D individuals. **Hypothesis:** T1D-Sleep-Opt-In will result in clinically significant increased sleep duration and regularity. **Approach:** Sleep duration and regularity will be measured by actigraphy at baseline, Week 4, Week 8, and post-program at Weeks 12 for both groups (and Week 24 T1D Sleep-Opt-In only).

Aim 3: Preliminary efficacy of T1D-Sleep-Opt-In on glycemic control. **Rationale:** Short sleep duration and sleep irregularities were associated with poor glycemic control in T1D. Sleep optimization in short-sleeping individuals without diabetes resulted in improved insulin resistance. **Hypothesis:** T1D-Sleep-Opt-In will result in improved glycemic control. **Approach:** A randomized controlled trial of an 8-week T1D-Sleep-Opt-In compared to an information control group on glycemic control, measured by A1C, fructosamine, and glucose variability from continuous glucose monitoring assessed at baseline, Weeks 4, 8, and post-program Week 12 for both groups (and Week 24 T1D Sleep-Opt-In only).

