optimization program to improve glycemic outcomes is novel. **(3) Effects on diabetes distress.** Diabetes distress is common and contributes to poor glycemic control and reduced quality of life. Sleep optimization offers a unique and practical treatment to reduce diabetes distress. **(4) Durability as determined by a follow-up period.** No data exist regarding the durability of sleep optimization. Understanding the long-lasting effects will lead to designing a reinforced intervention with proper timing and optimize the effects of T1D-Sleep-Opt-In.

T1D Sleep-Opt-In is unique, practical, and scalable. The proposed intervention is based on a theoretical model focused on motivating long-term behavior change. It uses technologies desirable to patients and already part of their daily lives. Using this combination of technology and well-validated behavior change strategies, we can engage patients to learn their behavioral patterns and make lasting changes in their sleep habits. The use of technology and automated support could result in a highly scalable and cost-effective intervention.

Approach

C.1 Preliminary Studies

C.1.1 Insufficient and irregular sleep are associated with poorer glycemic control in adults with T1D.

[name], co-PI of this study, published a meta-analysis exploring the role of sleep in T1D. In a pooled analysis of 533 adults, those reporting sleeping < 6h had a higher A1C level by 0.24% than those sleeping ≥ 6 h.³ [name] subsequent study explored the role of sleep variability using 5-day actigraphy in 41 adults with T1D.¹⁰ Those with higher sleep variability (standard deviation, SD, of sleep duration > 60 minutes) had significantly higher A1C levels than those with lower sleep variability (median 7.8% vs. 7.2%). In addition, higher sleep variability significantly correlated with higher daily insulin requirement ($r = 0.386, p = 0.01$), suggesting higher insulin resistance. [name], co-PI, studied 30 adults with T1D and found that variability of sleep duration as measured by actigraphy was significantly related to glycemic variability (glucose SD) measured by continuous glucose monitoring (CGM), $r = 0.458, p = 0.01$.

C.1.2 Sleep irregularity was associated with diabetes distress in T1D. In the same sample of 30 adults, greater sleep irregularity (sleep duration SD) significantly associated with diabetes distress ($r = .600, p < .001$).

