C.2.2 Participants. We plan to recruit 20 subjects. Inclusion criteria: working-age adults, 18-65 years with a clinical diagnosis of T1D for at least one year who reported habitual sleep duration <6.5h/night during work- or weekdays with a desire to sleep longer; own a smartphone compatible with Fitbit. Exclusion criteria: A1C \leq 10%, Insomnia symptoms defined as severe as assessed by the Insomnia Severity Index (score \geq 22), being at high risk for obstructive sleep apnea as assessed by Berlin Questionnaire,⁵⁶ history of severe hypoglycemia (defined as hypoglycemic episodes that result in loss of consciousness within the last 6 months, seizures, or requiring help from others), being treated with insulin pump with a hybrid closed-loop feature, rotating shift or night shift work, significant renal impairment (estimated glomerular filtration rate < 45 ml/min/1.73 m²), significant medical morbidities, such as congestive heart failure, cirrhosis, chronic obstructive pulmonary disease requiring oxygen, active treatment for cancer or psychiatric problem, history of stroke with neurological deficits, pregnant or planning pregnancy. Inclusion/exclusion criteria will be obtained by participant self-report on all criteria except the estimated glomerular filtration rate and A1C which will be obtained by a blood draw. Subjects will be recruited through the UIC medical center and local diabetes websites and organizations, using flyers, e-announcements, and recruitment letters. UIC endocrinology clinic serves approximately 4,000 patients with diabetes per year.

C.2.3 Subjective sleep assessment Participants will complete standardized questionnaires. The Pittsburgh Sleep Quality Index (PSQI) assesses sleep quality in the past month,⁵⁷ Epworth Sleepiness Scale (ESS) assesses daytime sleepiness,⁵⁸ Insomnia Severity Index (ISI) assesses insomnia symptoms,⁵⁹ and the Berlin questionnaire assesses risk of obstructive sleep apnea.⁵⁶ ISI and Berlin questionnaires will be used to screen for eligible participants. PSQI and ESS will be administered at baseline and Weeks 4, 8, 12 for both groups, (and week 24 T1D Sleep-Opt-In only).

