C.2.4 Wrist actigraphy to measure behavioral sleep Participants will wear an Actiwatch Spectrum Plus (Respironics, USA) on their non-dominant wrist for one week during baseline assessment, and Weeks 4, 8, 12 for both groups (and week 24 T1D Sleep-Opt-In only). Data will be collected in 30-sec epochs. Subjects will be asked to keep a daily sleep log and press an event marker on the Actiwatch at bedtime and wake-up time. Data will be downloaded and reviewed with each participant to clarify inconsistencies when the Actiwatch is returned. Rest intervals will be set using reported try-to-fall-asleep times and wake-up times on daily sleep logs or event markers if these times are missing. Using the Immobile Minutes algorithm in the Actiware 6 software, we will derive the following outcome variables: sleep onset, sleep offset, sleep duration, sleep efficiency (a measure of sleep quality), mid-sleep time (time point between sleep onset and wake time), and standard deviation (SD) of sleep duration, an indicator of sleep regularity which we previously showed to be related to glucose metabolism.¹⁰

C.2.5 Diabetes distress assessment. Diabetes distress will be measured with the Diabetes Distress Scale.⁶⁰ Additional related variables measured will be the CES-D, a measure of depression, the GAD-7, a

C.2.1 Proposed study overview. Table 2 illustrates the proposed study. We will first adapt our current sleep optimization to be T1D-specific (see C.2.8). We will then recruit 20 non-shift-working adults aged 18-65 years with a clinical diagnosis of T1D for at least one year who reported habitual sleep duration < 6.5h/night during work- or weekdays. After informed consent is obtained, participants will have a baseline assessment during a 1-week

measure of general anxiety,⁶² Fatigue PROMIS short-form 1a, Hypoglycemia Fear Survey and the Diabetes Self-Management Questionnaire. These variables will be measured at baseline, weeks 4, 8, 12 both groups (and 24 T1D Sleep-Opt-In only). Subjects who score 16 or greater on the CES-D will be offered a list of mental health resources (See Mood Score Script, Ver 1, 2-14-19 and Health Resources, Ver 1, 2-14-19).

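### Section C.2.2 excludes people with A1C at or below 10%, so as written only those above 10% can enter, a restriction that nothing else in the protocol states or explains

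*Combined protocol and SAP*

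**What the plan says.** The first item in the exclusion list of C.2.2 (Participants) is "Exclusion criteria: A1C \leq 10%, Insomnia symptoms defined as severe". The same section says that eligibility is self-reported for every criterion "except the estimated glomerular filtration rate and A1C which will be obtained by a blood draw". A1C is therefore one of only two criteria checked against a laboratory value. The inclusion list in C.2.2 contains no A1C condition.

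Elsewhere the population is described without reference to A1C:

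- Abstract: "we propose a randomized controlled trial in 20 adults aged 18 to 65 years with T1D", with screening for habitual sleep under 6.5 hours.
- Specific Aims, primary aim: "in working-age adults with T1D and habitual short sleep duration".
- Specific Aims, design statement: "This pilot study will randomize 20 working adults with T1D (18-65 years) who report habitual short sleep duration".
- C.2.1 (study overview): "recruit 20 non-shift-working adults aged 18-65 years with a clinical diagnosis of T1D for at least one year who reported habitual sleep duration" below 6.5 hours on work days or weekdays.

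In C.1.1, which gives the preliminary data on sleep variability and A1C in 41 adults with T1D, the group with more variable sleep "had significantly higher A1C levels than those with lower sleep variability (median 7.8% vs. 7.2"%).

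**The concern.** An exclusion of A1C at or below 10% leaves only A1C above 10% eligible. That would be a defining feature of the trial, yet no section mentions it or gives a reason for it.

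The rule is operative, because staff compare a blood result with this inequality. If they follow the text:

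- The Aim 1 feasibility data (C.2.7: numbers recruited, screened, eligible and consented) would reflect a very restrictive filter that the aims do not describe.
- A1C is the main glycemic measure (C.2.6), so the screening variable is also the Aim 3 outcome. Its baseline distribution would be cut off at 10%, and its mean, SD and change would not carry over to the population in the aims. C.2.10 intends the pilot to help with sample size for a larger trial.
- Selecting people for a high A1C exposes within-arm change to regression to the mean. This matters most for Week 24, where only the intervention arm is followed.

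If staff quietly reverse the sign, enrollment departs from the written criteria.

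**Working it through.** **1. The direction of the rule.** Excluded: A1C ≤ 10%. Eligible: A1C > 10%. This follows from the text with no assumption.

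**2. Comparison with the other thresholds in the list.** Severe insomnia is excluded at an Insomnia Severity Index score of 22 or more. Renal impairment is excluded at "estimated glomerular filtration rate < 45 ml/min/1.73". Both remove the more severe end of the scale and match their own descriptions (severe insomnia, significant renal impairment). The A1C item removes the lower end and carries no description. The insomnia threshold also shows that a greater-than-or-equal sign in the same list came through correctly, which makes a misread symbol less likely.

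**3. Search for a stated floor.** The abstract, Specific Aims, C.2.1 and the inclusion list in C.2.2 contain none. No passage gives a rationale for restricting entry to A1C above 10%.

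**4. Minimum share of the preliminary cohort excluded, without a distributional assumption.** At least half of each group lies at or below its own median (7.8% or 7.2%), and both medians are below 10%. With group sizes n1 + n2 = 41, one is odd and one even, so the minimum is ceil(n1/2) + ceil(n2/2) = 21. For example, groups of 20 and 21 give 10 + 11 = 21. This assumes that the two groups make up the whole cohort.

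**5. Illustration of scale.** The documents give no SD for A1C. Assume a normal distribution, use the two medians as means, and take SDs of 1.0 and 1.5, with 2.0 as a wider case.

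Share eligible: p = 1 − Φ((10 − mean)/SD). Expected A1C tests to find 20 eligible people: 20/p.

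| Mean | SD (assumed) | z | p | 20/p |
|---|---|---|---|---|
| 7.2% | 1.0 | 2.80 | 0.26% | 7,828 |
| 7.2% | 1.5 | 1.87 | 3.10% | 646 |
| 7.2% | 2.0 | 1.40 | 8.08% | 248 |
| 7.8% | 1.0 | 2.20 | 1.39% | 1,439 |
| 7.8% | 1.5 | 1.47 | 7.12% | 281 |
| 7.8% | 2.0 | 1.10 | 13.57% | 148 |

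The counts apply to people who already meet every other criterion.

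**6. What cannot be computed.** The size of regression to the mean depends on the within-person correlation of A1C between visits, which the documents do not give. The plan states no power, alpha or effect size that this point could change.

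**The case against.** Four objections deserve weight.

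- **The symbol may be an artefact of PDF text extraction.** It appears as a typesetting code, whereas other sections show the native character. Of the two comparison thresholds, only the insomnia score uses the same kind of symbol. This stands as a reason to look at the source PDF, but the correctly rendered sign in the same list makes a misread unlikely.
- **The abstract, aims and overview are summaries.** They omit most of the other exclusions too, such as sleep apnea risk and hybrid closed-loop pumps, so their silence on A1C is not in itself a contradiction. That is fair. The stronger evidence is that so severe a restriction has no stated reason anywhere.
- **The preliminary cohort does not set eligibility.** It is not described as selected for short sleep. Its medians make the literal rule implausible but do not formally contradict it. The test counts rest on assumed SDs and a normal tail, and vary widely.
- **The harm is conditional.** The documents include no screening form, and staff may not have applied the literal text. The trial is an unpowered pilot of 20. The randomized comparison through Week 12 is protected in expectation from regression to the mean.

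These points limit the supporting evidence and the claim of harm. They leave untouched the literal meaning of an eligibility rule that staff apply to a laboratory result.

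**Conclusion.** The concern holds and should be corrected. The literal rule in C.2.2 admits only people with A1C above 10%, and nothing in the protocol states or supports that restriction. This conclusion needs no distributional assumption; it depends only on the symbol being as printed.

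On scale, the firmest figure is at least 21 of the 41 preliminary participants ineligible. The eligible share of about 0.3% to 7.1% at SDs of 1.0 to 1.5, rising to 13.6% at SD 2.0, is illustrative only.

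If the rule is applied as written, the damage is to the feasibility counts, the A1C estimates for planning and the within-arm A1C changes. The documents do not show whether the inequality is reversed, an inclusion condition sits in the wrong list, or a floor was intended, and this review does not choose among them.

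**What to change.** 1. Check the symbol in the source PDF of C.2.2.
2. Reconcile the direction of the A1C inequality with the intended population. If the sign or the placement is wrong, correct it. If a floor was intended, state it as an inclusion criterion and revise the abstract, aims, overview and rationale to match.
3. Check that the screening form and screening log agree with the settled text. If screening has begun, establish which direction was applied and report the Aim 1 counts accordingly.

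The cost is a wording correction and a document check, with further edits to the aims and rationale only if a floor was intended. The sample size, visits and tests do not change.

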C.1.5 Our research team consists of investigators from multiple disciplines with expertise that will facilitate successful completion of the project. This application brings together an interdisciplinary team with shared (T1D, sleep, CGM technology and glycemic variability measures, chronic illness, and clinical practice) and complementary (behavioral coaching, technology-assisted behavior change, statistical modeling, and Certified Diabetes Educator [CDE®]) expertise. Collectively, the team's research strengths span conceptual, methodological, clinical, statistical, and research in self-management and chronic disease.

C.2 Research plan

		Actigraphy/ sleep questionnaire	CGM, fructosamine, HbA1c	Diabetes Distress	Feasibility/ Acceptability
20 T1D subjects	Baseline	X	X	X	
Randomization	4-week	X	X	X	
	8-week	X	X	X	X
Follow up	12-week	X	X	X	
	24-week	X	X	X	

Table 2: Study Overview

run-in phase. Subjective sleep (see C.2.3) and objective sleep assessment by wrist actigraphy (see C.2.4) will be performed. Diabetes distress will be assessed (see C.2.5). Glycemic assessments will be performed by A1C, serum fructosamine, and 1-week CGM (see C.2.6) and height, weight and waist circumference will be obtained. The participants will then be randomized 3:2 to either T1D-Sleep-Opt-In (see C.2.8) or attention control group for 8 weeks (see C.2.9). At Weeks 4 and 8, participants will have assessments of subjective and objective sleep, 1-week CGM, serum fructosamine, and diabetes distress. *Additionally, stool samples will be collected at week 0 and week 8 to measure the gut microbiome.* These measurements will be repeated at 12 for both groups- (and 24-week T1D Sleep-Opt-In only) follow-up visits to evaluate the program's durability. At the end of the intervention (Week 8), feasibility and acceptability will be determined (see C.2.7).

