C.2.6 Glycemic assessment Glycemic control will be primarily assessed by hemoglobin A1c (A1C; Quest Diagnostics), a gold standard marker of glycemic control in T1D reflecting average glucose levels in the previous 90 days. Secondary measures will include serum fructosamine (Quest Diagnostics) and CGM. Serum fructosamine is a glycated albumin that reflects glucose levels in the preceding three weeks and allows assessment of changes in glucose values in a shorter term than A1C. CGM (blinded) will be conducted using FreeStyle Libre Pro glucose sensor (FDA-approved). The sensor tracks glucose concentrations in the interstitial fluid over 24 h using a thin flexible filament (< 0.4 mm thick) inserted into the upper arm (5 mm depth). The system captures glucose levels every 1 minute and records the data every 15 minutes. Outcome variables derived from the CGM are mean glucose level, standard deviation (SD), coefficient of variation (CV), percentage of time spent < 70 mg/dl, and percentage of time spent ≥ 180 mg/dl.⁶³ Interstitial glucose measurements with FreeStyle Libre were found to be accurate compared with capillary blood glucose reference values.⁶⁴ Glycemic measures will be obtained for one week at baseline and Weeks 4, 8, 12 for both groups, (and week 24 T1D Sleep-Op-In group only). A small amount of serum or plasma (2 tsp) will be frozen and stored in a freezer at the College of Nursing for later analysis by UIC researchers.

C.2.6.1 Microbiome *Stool samples to measure the gut microbiome will be collected at week 0 and week 8. Changes in sleep may alter the gut microbiome and potentially influence glycemia. Participants will be provided a collection device (Easysampler®, ALPCO, Inc.) and return the specimen at a subsequent visit.* Remaining stool samples will be stored in a freezer at the College of Medicine for later analysis by UIC researchers.

C.2.7 Feasibility and acceptability of T1D-Sleep-Opt-In Feasibility will be determined through analysis of recruitment (number recruited, screened, eligible, and consented) and retention (% session participation, program completion rates). Acceptability will be determined through participant evaluation (written evaluation and interview at program completion). See Appendix B.

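### Do the undated Week 8 recording week and the 90-day reach of A1C spoil the Week 8 comparison?

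*Combined protocol and SAP*

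**What the plan says.** **Glycemic measures.** C.2.6 makes A1C the primary glycemic measure, "reflecting average glucose levels in the previous 90 days". Fructosamine and blinded CGM are secondary, and fructosamine is included because it "reflects glucose levels in the preceding three weeks and allows assessment of changes in glucose values in a shorter term than A1C". On timing, the section says "Glycemic measures will be obtained for one week at baseline and Weeks 4, 8, 12 for both groups". It gives no start day, end day or day of blood draw.

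**Actigraphy.** C.2.4 has the Actiwatch worn "for one week during baseline assessment, and Weeks 4, 8, 12 for both groups". C.2.8.1 makes actigraphy the measure of the main outcome.

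**Meaning of Week 8.** The opening summary writes "At completion (Week 8) and post-program, baseline measures will be repeated to determine differences between the two groups (Week 12", and C.2.1 writes "At the end of the intervention (Week 8), feasibility and acceptability will be determined". Both use Week 8 as a point in time. C.2.8.3 uses Weeks 4 to 8 as program weeks, during which bedtime reminders may be switched off. The aims and Table 2 place Week 12 after the program, as follow-up.

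**Visit text.** C.2.1 says "At Weeks 4 and 8, participants will have assessments of subjective and objective sleep, 1-week CGM, serum fructosamine, and diabetes distress", which does not name A1C. Table 2 has an HbA1c column marked at 4 and 8 weeks, and Aim 3 lists A1C at both.

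**Analysis.** C.2.10 is mainly descriptive. It fits an MMRM to try out the model for a larger trial, and it disclaims power for sleep, glycemic control and distress.

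**The concern.** A one-week recording attached to a visit can run up to that visit or away from it. At Week 8 the choice matters because the visit coincides with the end of coaching: one reading gives a week wholly on the program and the other a week wholly off it. If staff placed it after completion, or differently for different participants, the Week 8 contrast for the main sleep outcome and for CGM would not be an end-of-program contrast. Device dates would reveal this later but could not recover the lost week.

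The primary glycemic measure raises a second worry. A 90-day average taken 56 days after randomization still contains pre-randomization glucose, so it understates a sustained effect, and no sentence says how to read it beside the faster measures.

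Third, a reader of C.2.1 alone might conclude that A1C is not drawn at Weeks 4 and 8.

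**Working it through.** **Inputs.** A1C look-back of 90 days and fructosamine look-back of 21 days (C.2.6); program of 8 weeks = 56 days, 3:2 allocation of 20 = 12 versus 8 (C.2.1); A1C difference of 0.24 points by self-reported sleep duration (C.1.1).

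**Assumptions, not in the documents.** Randomization and program start are both day 0; each look-back day has equal weight unless stated; A1C SD is 0.6 to 1.2 points.

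**1. Recording week.** Overlap of a 7-day recording with program days 0 to 56:

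- days 49 to 56: 7/7 in the program;
- days 56 to 63: 0/7.

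With the same one-week shift, the Week 4 recording stays in the program and the Week 12 recording stays after it. Only Week 8 can change category.

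Which reading does the text support?

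- C.2.4 uses the word *during*, which points to the eighth week itself.
- C.2.8.3 counts Weeks 4 to 8 as program weeks.
- The summary, the aims and Table 2 separate Week 8 from post-program time, which begins at Week 12. A recording on days 56 to 63 would put Week 8 data in the category these places keep for later visits.
- The only recording that is explicitly placed, at baseline, is completed before the event it is tied to (randomization).

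The in-program reading is therefore the natural one, though no day is written down.

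**2. A1C look-back.** Pre-randomization share at draw day d = max(0, 90 − d)/90.

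| Visit | One week early | Nominal day | One week late |
|---|---|---|---|
| Week 4 | 69/90 = 76.7% | 62/90 = 68.9% | 55/90 = 61.1% |
| Week 8 | 41/90 = 45.6% | 34/90 = 37.8% | 27/90 = 30.0% |
| Week 12 | 13/90 = 14.4% | 6/90 = 6.7% | 0% |

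The 37.8% applies to a draw on exactly day 56, so it does not come from a loose window. It also depends on equal weighting: if weights decline linearly into the past, the share is (34/90)² = 14.3%.

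Fructosamine at day 56 covers days 35 to 56, which is 21/21 in the program. Even at day 63 it covers days 42 to 63, with 14/21 in the program and none before randomization.

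**3. Size against precision.** Suppose the whole 0.24 points applied from day 0. This is generous, because 0.24 is a cross-sectional difference and a gradual effect would show less. The Week 8 shortfall would be 0.24 × 0.300 = 0.07 to 0.24 × 0.456 = 0.11 points. The 95% half-width for a difference between 12 and 8 participants is 2.101 × √(1/12 + 1/8) = 2.101 × 0.456 = 0.96 SD. That is 0.58 points at SD 0.6 and 1.15 points at SD 1.2.

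**4. A1C in C.2.1.** Three places (Table 2, Aim 3, C.2.6) schedule A1C at Weeks 4 and 8. One sentence leaves it out, and it sits in a section that refers the reader to Table 2 for the study design.

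**The case for a change.** The best argument for a change is that a recording week has to be settled before data are collected, whereas interpretation can wait. The MMRM results are meant to help size a later trial, and follow-up visits are meant to show durability. If Week 8 is in truth post-program, the planning estimate is mislabelled and durability has no end-of-program reference. The text does not strictly exclude this: C.2.6 says *at* where C.2.4 says *during*, two sentences use Week 8 as the moment of completion, and a team that hands out devices at consent for the baseline week might repeat that pattern at the Week 8 visit.

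It is true that no start or end day is written and that a lost in-program week could not be recovered. But the weight of the text lies on the in-program side, and a coordinator planning an end-of-intervention assessment would be expected to schedule it that way. The schedule is common to both groups, so a shift would alter what the Week 8 contrast describes without making it unfair. Nothing in the documents shows that one week's displacement would move sleep or glucose appreciably.

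On A1C, the objection is that the dilution should be stated. C.2.6 already gives the 90-day reach and names fructosamine as the shorter-term measure, so the reader has what is needed.

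**Conclusion.** No change follows. The Week 8 recording week is a missing detail that staff and analysts would fill sensibly from the rest of the document, and the between-arm comparison holds on either reading provided both arms keep to the common schedule. The pre-randomization share of Week 8 A1C (37.8% with equal weights, 30.0% to 45.6% if the draw moves a week, about 14% with declining weights) is a property of the marker. The plan discloses the look-back and covers it with fructosamine, CGM and a Week 12 A1C, so a further sentence would alter no result. The missing mention of A1C in C.2.1 is a clerical slip, since three other places schedule it.

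The stakes are small. A dilution of 0.07 to 0.11 points on a generous assumed effect compares with an uncertainty of 0.58 to 1.15 points (SD assumed) in a descriptive pilot that claims no power. The conclusion would be weaker only if recordings were timed differently in the two arms, and nothing in the plan suggests that.
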